### **9.2 SAMPLE SIZE DETERMINATION**

A total of 32 Chinese participants will be enrolled in this study with 16 participants in each group of 40 mg and 80 mg baloxavir marboxil.

The number of participants (16 participants for each dose level) is chosen based on practical clinical judgment, the PK variability observed (AUC and  $C_{max}$  in Caucasian and Japanese healthy participants), anticipated drop-rate, and China's regulatory requirements.

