#### **9.4.4 Pharmacokinetic Analyses**

All participants who have received study drug and who have evaluable PK data with no relevant protocol deviations with respect to the primary PK endpoint will be included in the PK analysis population.

Analyses will be carried out on the PK analysis population.

Individual plasma concentrations at each sampling timepoint for baloxavir marboxil and its major metabolite, baloxavir will be presented by listings and appropriate descriptive summary statistics by dose, including arithmetic means, geometric means, medians, minimums-maximums, SD, and coefficients of variation. Individual and mean plasma concentration versus time data will be plotted by dose on linear as well as semi-logarithmic scales.

All PK parameters will be presented by individual listings and summary statistics by dose including arithmetic means, geometric means, medians, minimums-maximums, SDs, and coefficients of variation.

The primary baloxavir marboxil and baloxavir PK study parameters will be the  $C_{max}$  and the area under the concentration-time curve from Time 0 to infinity ( $AUC_{0-inf}$ ) if it can be derived accurately, otherwise a truncated as appropriate. All other PK parameters will be regarded as secondary.

Non-compartmental analysis using WinNonlin software will be used to calculate PK parameters where appropriate. Non-compartmental analysis will be employed for estimation of the following PK parameters:

- $T_{max}$ : Time to maximum observed plasma concentration
- $C_{max}$ : Maximum observed plasma concentration
- $AUC_{0-inf}$ : Area under the plasma concentration-time curve between Time 0 extrapolated to infinity
- $AUC_{0-last}$ : Area under the plasma concentration-time curve between Time 0 and the time of the last quantifiable concentration
- $AUC_{0-t}$ : Area under the plasma concentration-time curve between Time 0 and the time t. Time t may be chosen as a time point where evaluable concentrations are available in at least 90% of participants
- $t_{1/2}$ : Terminal elimination half-life
- $CL/F$ : Apparent total oral clearance

- Vz/F: Apparent oral volume of distribution based on the terminal phase
- Plasma concentration at 24, 48, and 72 hours postdose.

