16.2. PLASMA PHARMACOKINETIC PARAMETERS

Single-dose PK parameters for plasma baloxavir marboxil and its major metabolite, baloxavir, will be estimated by noncompartmental methods using actual elapsed time from dose administration in the final analysis. Subjects with partial data will be evaluated on a case-by-case basis to determine if sufficient data are available for reliable estimation of PK parameters.

The following data handling conventions for concentrations apply to the PK analysis:

- Pre-dose samples that are missing or BLQ will be assigned a numerical value of zero.
- Any pre-dose concentration values that are quantifiable will be included in the PK analysis. Concentrations and the calculated PK parameters shall be listed and included in the applicable summaries and inferential statistics. Profiles with anomalous pre-dose concentration value which is not greater than 5% of C_{max} will be evaluated. The presence of anomalous pre-dose concentration value greater than 5% of C_{max} in the profile will be evaluated on a case-by-case basis to determine if exclusion is warranted by the data.

Document: Roche_YP40902_SAP

Authors: [REDACTED], [REDACTED], [REDACTED]

Version Number: 2.2

Version Date: 06MAR2020

Template No.: CS_TP_BS016 Revision 5

Reference: CS_WI_BS005

Effective Date: 01Apr2018

F. Hoffmann-La Roche Ltd and Shionogi & Co., Ltd
PROTOCOL YP40902

Statistical Analysis Plan

Page 19 of 31

- Post-dose BLQ concentrations will be assigned a value of zero if they precede quantifiable data points in the initial portion of the profile (before C_{max}).
- A BLQ value that occurs between quantifiable data points, especially prior to C_{max} will be evaluated to determine if an assigned concentration of zero makes sense, or if reanalysis or exclusion of the data is warranted.
- Following C_{max} , BLQ values embedded between 2 quantifiable data points will be treated as missing.
- Trailing BLQ values at the end of the collection interval (after the last quantifiable concentration) will be set to zero.
- If consecutive BLQ concentrations are followed by quantifiable concentrations in the terminal portion of the concentration curve, these quantifiable values will be set to missing (blank data) and excluded from the PK analysis, unless otherwise warranted by the concentration time profile.

Handling of PK Concentration Values From Subjects Who Vomit:

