- If a subject vomits at or before the 12th hour following dosing, only their PK concentration values up to the emesis event will be included in the PK concentration summary. If a subject vomits after the 12th hour following dosing, all their PK concentration values will be included in the PK concentration summary.

The molecular formula and molecular weight (MW) for each analyte are listed below:

- Baloxavir marboxil:
- Molecular Formula: $C_{27}H_{23}F_2N_3O_7S$
- Molecular Weight: 571.55 Da

- Baloxavir:
- Molecular Formula: $C_{25}H_{19}F_2N_3O_4S$
- Molecular Weight: 495.55 Da

Based on clinical PK data to date from Caucasian and Japanese subjects, baloxavir plasma concentrations have not been quantifiable in any of the collected samples. The same observation is anticipated in the current study. As such, the metabolite-to-parent exposure ratios (MRC_{max} and MRAUC_{0-inf}) will only be calculated if there is detectable

Document: Roche_YP40902_SAP

Authors: [REDACTED], [REDACTED], [REDACTED]

Version Number: 2.2

Version Date: 06MAR2020

Template No.: CS_TP_BS016 Revision 5

Reference: CS_WI_BS005

Effective Date: 01April2018

baloxavir plasma levels within the profile. MRC_{max} will be calculated if the profile contains 1 or more quantifiable baloxavir concentration; whereas a minimum of 4 quantifiable baloxavir concentrations are required for the calculation of MRAUC_{0-inf}.

The following PK parameters will be calculated for both analytes where estimable, unless otherwise indicated:

C _{max} (ng/mL)	Maximum observed plasma concentration obtained directly from the concentration versus time data.
T _{max} (h)	Time to maximum observed plasma concentration, obtained directly from the observed concentration versus time data.
AUC _{0-inf} (ng·h/mL)	Area under the concentration-time curve in plasma from zero (pre-dose) extrapolated to infinite time, extrapolated to infinity by addition of the last observed quantifiable concentration divided by the elimination rate constant: AUC _{0-last} + C _{last} /λ _z .
AUC _{0-last} (ng·h/mL)	Area under the concentration-time curve in plasma from zero (pre-dose) to the time of the last quantifiable concentration.
AUC _{0-t} (ng·h/mL)	Area under the concentration-time curve in plasma from zero (pre-dose) to time t. Time t may be chosen as the latest common time point where evaluable concentrations are available in at least 90% of participants.

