λ _z (1/h)	Apparent terminal rate constant, determined by linear regression of the terminal log-linear segment concentration-time curve.
t _{1/2} (h)	Apparent terminal elimination half-life, determined as: ln2/λ _z .
CL/F (L/h)	Apparent systemic clearance after oral dosing, calculated for baloxavir marboxil only as follows: Dose/AUC _{0-inf} .
V _z /F (L)	Apparent volume of distribution following oral dosing based on the terminal phase, calculated for baloxavir marboxil only as follows: Dose/(λ _z ·AUC _{0-inf}).
C ₂₄ (ng/mL)	Observed plasma concentration at scheduled 24 hour post-dose sample.
C ₄₈ (ng/mL)	Observed plasma concentration at scheduled 48 hour post-dose sample.
C ₇₂ (ng/mL)	Observed plasma concentration at scheduled 72 hour post-dose sample.

Document: Roche_YP40902_SAP

Authors: [REDACTED], [REDACTED], [REDACTED]

Version Number: 2.2

Version Date: 06MAR2020

Reference: CS_WI_BS005

Template No.: CS_TP_BS016 Revision 5

Effective Date: 01Apr2018

MRC_{max} Mole ratio of metabolite C_{max} to parent (baloxavir marboxil) C_{max}, calculated as follows:

$$\text{MRC}_{\text{max}}: \frac{\text{baloxavir } C_{\text{max}}}{\text{baloxavir marboxil } C_{\text{max}}} \times \frac{\text{baloxavir marboxil MW}}{\text{baloxavir MW}}$$

MRAUC_{0-inf} Mole ratio of metabolite AUC_{0-inf} to parent (baloxavir marboxil) AUC_{0-inf}, calculated as follows:

$$\text{MRAUC}_{0-\text{inf}}: \frac{\text{baloxavir } AUC_{0-\text{inf}}}{\text{baloxavir marboxil } AUC_{0-\text{inf}}} \times \frac{\text{baloxavir marboxil MW}}{\text{baloxavir MW}}$$

The following PK parameters will be calculated for diagnostic purposes and listed but will not be summarized.

t_{1/2}, Interval The time interval (h) of the log-linear regression to determine λ_z

t_{1/2}, N Number of data points included in the log-linear regression analysis to determine λ_z.

Rsq Goodness of fit statistic for calculation of λ_z.

%AUC_{ex} Percentage of AUC_{0-inf} obtained by extrapolation, calculated as [(C_{last}/λ_z)/AUC_{0-inf} × 100].

Areas under the curve (AUCs) will be calculated by linear up/log down trapezoidal summation, where at least 3 quantifiable post-dose concentrations are available for AUCs. If the %AUC_{ex} is >30.0% of AUC_{0-inf}, then the corresponding individual subject number will be flagged with an asterisk “*” in the listing; AUC_{0-inf} and related parameters will not be included in the applicable summaries and inferential statistics.

For partial AUC (AUC_{0-t}):

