- If concentration at the end of the interval is available but collection time is missing, partial AUC will be calculated using scheduled time. In this case, the partial AUC estimate will be listed only and flagged for exclusion from the summaries and inferential statistics.
- If concentration at the end of the interval is the first BLQ value, partial AUC will be calculated (i.e. represents AUC_{all}). If concentration at the end of the interval is a later consecutive BLQ value, the partial AUC will not be calculated.

Visual assessment will be used to identify the terminal log-linear segment of the concentration-time curve for λ_z calculation. A minimum of 3 data points will be used for determination. If Rsq <0.800, λ_z and related parameters will be listed only.

The nominal dose (e.g., 40 mg or 80 mg) will be used for calculation of baloxavir marboxil dose-dependent PK parameters (CL/F and V_z/F).

For each analyte, individual PK parameters will be listed and summarized by dose levels using descriptive statistics, as described in [Section 6.1](#).

Document: Roche_YP40902_SAP

Authors: [REDACTED], [REDACTED], [REDACTED]

Version Number: 2.2

Version Date: 06MAR2020

Template No.: CS_TP_BS016 Revision 5

Reference: CS_WI_BS005

Effective Date: 01Apr2018

[REDACTED]

F. Hoffmann-La Roche Ltd and Shionogi & Co., Ltd
PROTOCOL YP40902

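### SAP 16.2 withholds AUC0-t from participants with two or more trailing BLQ values at time t, although its own zero rule defines that area; the result is a small upward bias in the baloxavir AUC0-t summary, mainly at 40 mg

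*SAP*

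**What the plan says.** SAP Section 16.2 gives two rules for AUC0-t when the end-of-interval sample is BLQ. For a first BLQ: "If concentration at the end of the interval is the first BLQ value, partial AUC will be calculated", and the SAP identifies the result with AUCall. For any later one: "If concentration at the end of the interval is a later consecutive BLQ value, the partial AUC will not be calculated".

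The data-handling conventions earlier in the same section state: "Trailing BLQ values at the end of the collection interval (after the last quantifiable concentration) will be set to zero". AUCs are "calculated by linear up/log down trapezoidal summation", "where at least 3 quantifiable post-dose concentrations are available for AUCs".

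On the choice of t, the parameter table in SAP 16.2 says: "Time t may be chosen as the latest common time point where evaluable concentrations are available in at least 90% of participants". It does not say whether a BLQ result is evaluable, or whether the 90% applies to all participants or to each dose group.

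Protocol Section 3 (Table 3) lists AUC0-t under the primary objective. Protocol 9.4.4 names Cmax and AUC0-inf as the primary parameters, the latter "if it can be derived accurately, otherwise a truncated as appropriate", and calls all other parameters secondary.

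**The concern.** Two participants can have the same area to t under the SAP's conventions, yet one is summarised and the other is not. What separates them is whether the first trailing BLQ falls at t or at an earlier sample. The participant who is left out is the one whose concentrations fell sooner, through lower exposure or faster elimination. The omission therefore depends on the quantity being summarised. SAP 7.3 (missing data) deals only with medication dates, and no sensitivity analysis covers this case.

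The two dose groups are not equally exposed to the rule. Protocol 2.2 describes baloxavir exposure as generally dose-proportional, so a 40 mg profile reaches any given limit about one half-life before an 80 mg profile.

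At stake are a listed endpoint and a possible substitute for the primary AUC, in a study whose PK results are to be compared with Japanese and Caucasian data (Protocol 2.2 and 4.3).

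**Working it through.** The documents give no figure for this bias, so there is nothing to reproduce.

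**Inputs from the documents.** The sample size is "16 participants in each group of 40 mg and 80 mg baloxavir marboxil" (Protocol 9.2). The baloxavir half-life is 79.1 h and its Tmax 4 h (Protocol 2.2). Late PK samples are at 120, 168, 216 and 264 h, then Day 15, which Protocol Table 1 puts at 336 h and Table 2 at 312 h. The BLQ and AUC rules are those of SAP 16.2.

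**Assumed, because not in the documents.** The lower limit of quantitation (LLOQ), the between-subject CVs, an absorption rate of 0.9/h, and the linear trapezoid for the segment that ends at zero (a log trapezoid cannot end at zero).

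**1. Are the two areas equal?** Take one profile with half-life 45 h, peak scale 100 and LLOQ 3. The last quantifiable sample is at 216 h and the first BLQ at 264 h.

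- AUC to 216 h = 6251
- AUC0-264 = 6338 (the SAP calculates this)
- AUC0-336 = 6338 + 72 × (0 + 0)/2 = 6338 (the SAP does not calculate this)

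Without an LLOQ the area to 336 h is 6450. The zero convention understates it by 1 − 6338/6450 = 1.7%.

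**2. Why 40 mg first?** Halving the dose brings the crossing of a fixed LLOQ forward by one half-life, 79.1 h. Samples from 120 to 264 h are 48 h apart. That shift is enough to turn a first BLQ at t into a later one.

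**3. How many can be lost if evaluable means quantifiable?**

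- 90% over all 32: ceil(0.9 × 32) = 29, so at most 3, possibly all at 40 mg
- 90% per group: ceil(0.9 × 16) = 15, so at most 1

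**4. Upper bound.** Suppose those lost have the lowest AUCs of 16. On the log scale, dropping the lowest 1 or 3 raises the mean by 0.118 or 0.311 SD. The inflation of the geometric mean is exp(shift × √ln(1 + CV²)) − 1, evaluated with unrounded shifts.

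| Assumed CV | lowest 1 lost | lowest 3 lost |
|---|---|---|
| 20% | 2.4% | 6.3% |
| 30% | 3.5% | 9.6% |
| 40% | 4.6% | 12.7% |

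**5. Expected size.** This step simulated 400 trials per scenario, each with 16 + 16 one-compartment baloxavir profiles. Median half-life was 79.1 h, exposure CV 30%, and the last sample at 336 h. LLOQ is a percentage of the 40 mg peak scale. Bias compares the 40 mg geometric mean under the SAP rule with the mean when everyone is kept.

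| Choice of t | half-life CV | LLOQ 1 / 3 / 5 / 8%: bias (%) | mean lost of 16 at 40 mg | mean lost of 16 at 80 mg |
|---|---|---|---|---|
| 90% rule on quantifiable samples, all 32 | 15% | 0.00 / 0.35 / 0.44 / 0.64 | 0.00 / 0.07 / 0.09 / 0.13 | 0.00 / 0.00 / 0.00 / 0.01 |
| same | 30% | 0.72 / 1.72 / 1.73 / 1.44 | 0.14 / 0.34 / 0.35 / 0.26 | 0.03 / 0.05 / 0.08 / 0.03 |
| t fixed at 336 h | 15% | 0.00 / 0.56 / 4.75 / 18.42 | 0.00 / 0.11 / 1.26 / 5.13 | 0.00 / 0.00 / 0.05 / 0.55 |
| same | 30% | 0.92 / 6.10 / 13.94 / 27.28 | 0.18 / 1.37 / 3.31 / 6.46 | 0.05 / 0.35 / 1.05 / 2.27 |

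The last two rows show what follows if BLQ results count as evaluable, so that t can move to the last sample. No scenario gave a downward bias. Selection acts on late concentrations, so the lost participants tend to have the lowest AUCs but need not.

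**6. Is the fallback likely to be needed?** At a 79.1 h half-life, the fraction remaining is 2^(−336/79.1) = 5.3%, or 2^(−312/79.1) = 6.5% if Day 15 is at 312 h. The extrapolated share of AUC0-inf is then of that order, far below the 30% at which SAP 16.2 removes AUC0-inf from the summaries.

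**The case against.** The case for leaving the rule alone has real substance.

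- **The 90% criterion already protects t.** Read as quantifiable, which is its evident purpose, it keeps t early enough that few are lost, and participants whose first BLQ is at t are kept. This stands, and it is why the expected bias is small. The criterion is optional, however, and the term is undefined.
- **AUC0-inf will probably serve as the primary parameter.** This stands (step 6). Protocol 9.4.4 also does not name AUC0-t as the substitute, and AUC0-last is untouched by the rule. But AUC0-last ends at a different time in each participant, so it does not replace an area to a common time.
- **No test is affected.** SAP 6.7 plans none. SAP 6.1 reports n for each parameter, so omissions can be seen. That shows the loss but does not correct the mean.
- **The zero convention slightly understates the area.** True, by 1.7% in the example, but the SAP accepts the same understatement one sample earlier.

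A reader might infer that the rule bears most on baloxavir marboxil, because it is extensively converted, and could leave that analyte with no AUC0-t at all. The documents do not support this. SAP 16.2 expects one analyte to be unquantifiable in every sample. It prints the name baloxavir, but given the Tmax and half-life in Protocol 2.2 it evidently means the parent. Such an analyte fails the three-sample minimum for any AUC, with or without this rule.

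**Conclusion.** The inconsistency is real and minor. SAP 16.2 calculates AUC0-t at the first trailing BLQ and refuses it at a later one, although its zero convention makes the areas equal. The resulting omissions push the baloxavir AUC0-t summary upward, and the 40 mg group loses more participants than the 80 mg group.

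With t set by the 90% criterion on quantifiable samples, the expected bias at 40 mg is about 0 to 2%. It is nil if no participant is BLQ before t. The size rests on the assumed LLOQ, CVs and profile shape.

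It would be tempting to read the 6 to 13% as the likely inflation of the study's primary AUC. That is not supported. It requires all three permitted participants to be at 40 mg, to have the three lowest AUCs, and to be BLQ both at t and at the sample before. It also concerns AUC0-t, which would matter as a primary measure only if AUC0-inf could not be used. Simulated biases up to 27% arise only when t is pushed to the last sample without the 90% safeguard.

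**What to change.** In the partial-AUC bullet of SAP 16.2, replace the second sentence with wording such as:

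> If the concentration at t is a later consecutive trailing BLQ, AUC0-t is the AUC to the first trailing BLQ (AUCall, trailing BLQ = 0) and is included in the summaries, provided at least 3 post-dose concentrations are quantifiable.

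In the definition of AUC0-t, state that t is chosen separately for each analyte, on quantifiable concentrations, and is common to both dose groups.

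The cost is two SAP edits and one programming rule; no further data are needed. AUC0-t may come out slightly lower and more variable, mainly at 40 mg, and it carries the slight understatement of the zero convention for the participants now included.

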17. SAFETY OUTCOMES

All outputs for safety outcomes will be based on the Safety Analysis Set (SAF).

There will be no statistical comparisons between the treatment groups for safety data, unless otherwise specified with the relevant section.

17.1. ADVERSE EVENTS

Adverse Events (AEs) will be coded using Medical Dictionary for Regulatory Activities (MedDRA) central coding dictionary, Version 22.0.

An overall summary of number of subjects within each of the categories described in the sub-section below, will be provided as specified in the templates.

Listings will include .

17.1.1. ALL AEs

Incidence of AEs will be presented by System Organ Class (SOC) and Preferred Term (PT) and also broken down further by maximum severity and relationship to study medication.

17.1.1.1. Severity

Severity is classed as mild/ moderate/ severe (increasing severity). If a subject reports an AE more than once within that SOC/ PT, the AE with the worst-case severity will be used in the corresponding severity summaries.

17.1.1.2. Relationship to Study Medication

Relationship, as indicated by the Investigator, is classed as 'not related' and 'related' (increasing severity of relationship). A 'related' AE is defined as an AE with a relationship to study medication as 'related' to study medication. AEs with a missing relationship to study medication will be regarded as 'related' to study medication. If a subject reports the same AE more than once within that SOC/ PT, the AE with the worst-case relationship to study medication will be used in the corresponding relationship summaries.

Document: Roche_YP40902_SAP

Authors: [REDACTED], [REDACTED], [REDACTED]

Version Number: 2.2

Version Date: 06MAR2020

Template No.: CS_TP_BS016 Revision 5

Reference: CS_WI_BS005

Effective Date: 01Apr2018

17.1.2. SERIOUS ADVERSE EVENTS

Serious adverse events (SAEs) are those events recorded as 'Serious' on the Adverse Events page of the (e)CRF. A summary of serious AEs by SOC and PT will be prepared.

17.1.3. ADVERSE EVENTS LEADING TO DEATH

AEs leading to Death are those events which are recorded as 'Fatal' on the Adverse Events page of the (e)CRF. A summary of AEs leading to death by SOC and PT will be prepared.

17.2. DEATHS

If any subjects die during the study as recorded on the 'End of study' page of the (e)CRF with 'Death' selected, the information will be presented in a summary table and a data listing.

17.3. LABORATORY EVALUATIONS

Results from the local laboratory will be included in the reporting of this study for Hematology, Clinical Chemistry, Urinalysis, Coagulation, Thyroid Functions, Lipid Profiles. The test details can be found in Appendix 4, [Table 7](#) of the protocol.

Presentations will use SI Units.

Quantitative laboratory measurements reported as "< X", i.e. below the lower limit of quantification (BLQ), or "> X", i.e. above the upper limit of quantification (ULQ), will be converted to X for the purpose of quantitative summaries, but will be presented as recorded, i.e. as "< X" or "> X" in the listings.

In the case of a retest (same visit number assigned), the latest available measurement for that visit will be used for by-visit summaries. The following summaries will be provided for laboratory data:

- Actual and change from baseline by visit (for quantitative measurements)
- Incidence of abnormal values according to normal range criteria (for quantitative measurements)
- Shift from baseline to worst value by Investigator's Assessment

Document: Roche_YP40902_SAP

Authors: [REDACTED], [REDACTED], [REDACTED]

Version Number: 2.2

Version Date: 06MAR2020

Template No.: CS_TP_BS016 Revision 5

Reference: CS_WI_BS005

Effective Date: 01April2018

[REDACTED]

